#### Follow-Up Visits

The determination of the study endpoints will require rigorous clinical follow-up and quality data collection. The Investigator or delegated study personnel will ensure the patient is scheduled for follow-up visits according to Table 5.

Table 4. Follow-up Visit Windows

Follow-Up Visit	Visit Window (days following Procedure)
30 Day	30 days, +14 days
6 Month	180 days +/-30 days
1 Year	365 days +/-60 days
2 Year	730 days +/-60 days
3 Year	1095 days +/-60 days
4 Year	1460 days +/-60 days
5 Year	1825 days +/-60 days

The importance of attending the 30 Day follow-up visit should be discussed with the patient. Planned absences should be recorded to facilitate continued ability to contact a study patient during the course of the study. If a patient cannot be reached for a follow-up visit, the investigator will document on the follow-up data form, the efforts undertaken to contact the patient, referring physicians, including internists as well as cardiologists, family members, or other alternate contacts noted in the study patient's records. These efforts should include 3 attempts of telephone contacts at separate dates and times, and a registered letter. If a patient can no longer be located, the investigator must contact an intermediary (e.g. patient's private physician) without delay.

Patients for whom the study procedure was begun but do not receive and retain the study valve will be followed up until the 30-day assessment or resolution of any AE for safety purposes. Patients with an ongoing AE at the 30 Day visit should have AEs reassessed at 30 day window closure (day 44). These patients should then be exited from the study. In the event that the patient's implanted

valve is explanted, the patient needs to be followed up until resolution of any AE for safety purposes. These patients should then be exited from the study.

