### 7.1.4 Selection of subjects (including selection of control group if necessary)

To ensure that a minimum of 50 patients are implanted with the SAPIEN 3 THV and complete the 30 Day follow-up for Primary Endpoint, up to 60 patients will be enrolled and implanted with SAPIEN 3 THV. Each site may not contribute more than 25 implanted patients to the study population. All patients will be followed for 5 years.

Enrolment will be closely monitored to ensure not more than 60 patients are implanted with SAPIEN 3 THV.

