### 8.4 Statistical method for all data, together with deficient, unused or fault data (including drop out and withdrawal) and method for treating unreasonable data

The primary and secondary endpoints will be reported based on the AT Population. Descriptive and summary statistical analysis will be performed on all endpoints. Patient listings for adverse events, deaths, and reinterventions will include all enrolled patients.

All clinically relevant baseline and follow-up variables will be tabulated. Descriptive statistics for continuous variables include mean, standard deviation, sample size, median, minimum, and maximum) and frequency tables or proportions for discrete variables.

Kaplan Meier estimates will be performed at the pre-specified follow-up times to project the estimates for time-related endpoints such as the 30-day mortality rate, the primary endpoint; the standard error and confidence limits will be computed using Greenwood's algorithm. Based on 50 patients as point estimate and length of estimate on the primary endpoint, the 30 days death rate and 95% confidence interval will be summarized.

Echocardiographic data will be analyzed by an Echo core laboratory with respect to the degree of total aortic valve regurgitation (TVR) and paravalvular aortic valve regurgitation (PAR) according to the VARC-2 definitions [29].

These data and other categorical data (e.g., NYHA class) will also be presented as shift from baseline for each of the pre-specified follow-up periods.

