#### Analysis Sets

- *As Treated (AT) Population*: all patients that were enrolled in the trial for whom the SAPIEN 3 valve implant procedure was begun, defined as the time in which the first Edwards' investigational device is inserted into the patient.

- *Valve Implant (VI) Population:* all AT patient who received and retained the SAPIEN 3 valve upon leaving the procedure room

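### Patients whose implant fails or is explanted leave follow-up by rule, so any As Treated survival estimate beyond 30 days would censor them because of device failure

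*Combined protocol and SAP*

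**What the plan says.** Four parts of the protocol bear on this.

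- **Exit rule** (Section 7.1.5.2, Follow-Up Visits). "Patients for whom the study procedure was begun but do not receive and retain the study valve will be followed up until the 30-day assessment" (alternatively, until adverse events have resolved). Those with an adverse event still ongoing at that 30-day visit "should have AEs reassessed at 30 day window closure (day 44). These patients should then be exited from the study". If an implanted valve is explanted, "the patient needs to be followed up until resolution of any AE for safety purposes", and is then also exited; no day limit is given.
- **General follow-up rule** (Section 7.1.4). "All patients will be followed for 5 years". The sentence has no qualifier. The 6 Month, 1 Year and 2-5 Year visit paragraphs likewise apply their assessments to all patients.
- **Population** (Sections 8.4 and 8.6). "The primary and secondary endpoints will be reported based on the AT Population". AT is "all patients that were enrolled in the trial for whom the SAPIEN 3 valve implant procedure was begun", counted from insertion of the first investigational device, so failed implant attempts are included. The Valve Implant (VI) set, AT patients who left the procedure room with the valve, is defined but no analysis is assigned to it.
- **Estimates** (Section 8.4). "Kaplan Meier estimates will be performed at the pre-specified follow-up times". The 30-day mortality rate is given as an example. Follow-up windows in Section 7.1.5.2 run to 5 years. No population or censoring rule is stated for any estimate after day 30.

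**The concern.** A patient who enters AT and does not keep the valve is taken out of observation because of how the procedure ended, not for an administrative reason. An AT Kaplan-Meier estimate at 6 months or later would treat that patient as censored. It would thereby assume that the patient's later risk equals that of patients who remain under follow-up with the valve in place. Nothing in the documents supports that assumption. If prognosis after a failed implant or an explant is worse, late mortality is understated, and by a mechanism that the protocol itself creates. Vital status is hard to recover once a patient has been exited, so the matter has to be settled before exits occur.

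**Working it through.** **The plan's nearest figure.** No stated number supports or contradicts the exit rule. The only derived figure nearby is the drop-out rate in Section 8.3: (60 − 50)/60 = 16.7%, which agrees with the stated <17%. It concerns completion of the 30-day visit and says nothing about later exits.

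**Day 30.** The visit window is 30 days with +14 days only, and patients without a valve are followed to the 30-day assessment. If that is honoured, day-30 AT mortality is unchanged. One ambiguity remains: the exit rule joins the 30-day assessment and resolution of adverse events with *or*, and does not say which governs if events resolve before day 30.

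**Size after day 30.** Let n = 60 patients have a retained valve (the maximum in Section 7.1.4) and k be AT patients without one. Section 7.1.5.1 counts only patients leaving with a valve toward the 60, so N = 60 + k. All mortality rates below are assumptions.

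- Day-30 mortality: 5% implanted, 15% failed implants.
- 1-year mortality: 15% implanted, 30% to 50% failed implants.
- 5-year mortality: 55% implanted, 75% to 90% failed implants.

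With failed implants censored just after day 30:

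- Reported survival = S30(all AT) × S(t)/S30 among the implanted.
- Full follow-up survival = [60 × S(t) implanted + k × S(t) failed]/N.
- Understatement of mortality = reported survival − full follow-up survival.

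Example, k = 3, 1 year, failed-implant mortality 50%:

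- S30(all AT) = (60 × 0.95 + 3 × 0.85)/63 = 0.9452.
- Reported mortality = 1 − 0.9452 × (0.85/0.95) = 15.4%.
- Full mortality = (60 × 0.15 + 3 × 0.50)/63 = 16.7%.
- Understatement = 1.24 points (from unrounded values).

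Understatement in percentage points:

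| k (N) | 1 year, failures 30–50% | 1 year, all failures dead | 5 years, failures 75–90% | 5 years, all failures dead |
|---|---|---|---|---|
| 1 (61) | 0.10–0.43 | 1.25 | 0.25–0.50 | 0.66 |
| 3 (63) | 0.29–1.24 | 3.62 | 0.73–1.44 | 1.92 |
| 5 (65) | 0.47–2.00 | 5.85 | 1.17–2.33 | 3.10 |

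The *all failures dead* columns keep the 15% day-30 mortality and let every remaining failed-implant patient die by that time. If failed-implant patients have the same mortality as implanted patients throughout, the understatement is 0.

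**Scale.** The simple binomial 95% half-width at n = 60 is 1.96 × √(0.15 × 0.85/60) = 9.0 points at 15% mortality and 1.96 × √(0.55 × 0.45/60) = 12.6 points at 55%.

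**Explants.** These are not in the calculation, because the documents give neither their frequency nor their timing. They left the procedure room with a valve, so they belong to both AT and VI.

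**The case against.** The strongest reply is that no specified endpoint is touched. Section 8.4 assigns AT to the primary and secondary endpoints, and every one in Section 7.1.6 is procedural or falls at 72 hours or 30 days. Section 7.1.5.2 separates visits to 30 days, for endpoint analysis, from later long-term data. Section 8.5 leaves detailed methods to a separate SAP whose text was not available for this review. The 5-year sentence closes a paragraph largely about implanted patients (the sentence before it reads "Each site may not contribute more than 25 implanted patients to the study population"), and the exit rule can be read as its specific exception.

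Much of this stands. A reader might infer that the plan specifies AT mortality curves from 6 months to 5 years; it does not do so expressly. The later estimates are a fair reading, because 30-day mortality is only an example and AT is the only analysis set named, but they remain a reading.

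Three further inferences are also unsupported:

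- *That the AT curve becomes the VI curve after day 44.* Deaths among failed implants before exit stay in the AT curve and carry through S30(all AT) to every later time.
- *That the gap must grow with time.* With k = 3, the all-dead figure falls from 3.62 points at 1 year to 1.92 at 5 years.
- *That every procedural mishap leads to exit.* A patient whose first valve embolises but who leaves with a second SAPIEN 3 in place appears to meet the VI definition and would stay in follow-up.

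What the reply does not remove is the literal conflict between sections, or the absence of a population and censoring rule for estimates beyond day 30. The narrower reading of Section 7.1.4 is possible, but that paragraph specifies implanted patients where it means them and does not do so in the 5-year sentence.

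**Conclusion.** The point holds in a limited form. The exit rules conflict with the unqualified 5-year and all-patient wording, and any AT survival estimate after day 30 would be censored by implant failure or explant. For 1 to 5 failed implants the understatement is about 0.1 to 2.0 points at 1 year and 0.3 to 2.3 points at 5 years. These figures rest wholly on assumed failure counts and mortality rates. The direction also depends on failed-implant patients having the worse prognosis after day 30, which the documents do not establish. The likely bias is well inside the sampling error of a study of about 60 patients. Severity is low to moderate: the case for acting is that the contradiction is clear, the remedy is cheap and the data are hard to recover later.

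**What to change.** 1. Reconcile Section 7.1.4 and the 6 Month, 1 Year and 2-5 Year visit paragraphs with the exit rules in Follow-Up Visits.
2. Keep the end of scheduled visits and imaging for patients without a retained valve and for explanted patients, but collect vital status by telephone or record at 6 months and yearly to 5 years for all AT patients, explants included. The 6 Month Visit already accepts telephone contact.
3. State in Section 8.4 or the SAP that every AT survival estimate after day 30 uses these data, and give the population and censoring rule.
4. Make clear that vital status at day 30 is obtained for every AT patient even if adverse events resolve earlier.

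If item 2 is not adopted, label estimates after day 30 as conditional on a retained, non-explanted valve and state the censoring rule. Relabelling them as Valve Implant is not enough, because explanted patients are in that set and are also exited.

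Cost: six contacts per affected patient (6 months and years 1 to 5), so at most 30 for five patients, plus consent wording. The labelling alternative needs only a text change.

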### 30-Day Visit

All patients will undergo the following assessments within the 30-Day follow-up period +14 days):

- Pertinent physical examination [include blood pressure, weight and all major systems findings]
- Adverse events
- Current cardiac medications and all medications given for cardiovascular effect
- NYHA functional classification
- CSS Angina Classification
- Neurological assessments
  - NIHSS
  - mRS
- 6 Minute Walk Test (6MWT)
- KCCQ
- Clinical Laboratory Test
  - Blood count (hemoglobin, hematocrit, platelet count, white blood cells)
  - Creatinine
  - CK/CK-MB and/or troponins
  - Albumin
- 12-Lead ECG
- Comprehensive TTE. If not adequate, a TEE will be performed

For patients with abnormal findings related to valve integrity and position and patients with adverse events related to worsening valve function, fluoroscopic imaging of the implanted valve will be completed.

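### The exit rule for explanted patients names no minimum day, so it may permit exit before 30-day vital status is known

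*Combined protocol and SAP*

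**What the plan says.** Follow-Up Visits (within Section 7.1.5.2) contains two exit rules.

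- **Procedure begun, valve not received and retained.** These patients "will be followed up until the 30-day assessment or resolution of any AE for safety purposes". The next sentence adds a recheck: "Patients with an ongoing AE at the 30 Day visit should have AEs reassessed at 30 day window closure (day 44"). They then leave the study.
- **Valve later explanted.** If the implanted "valve is explanted, the patient needs to be followed up until resolution of any AE for safety purposes", after which the patient is exited. Neither day 30 nor day 44 is mentioned.

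The 30-Day Visit section is general: "All patients will undergo the following assessments within the 30-Day follow-up period" (a window of 30 to 44 days).

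On the analysis side, Section 8.4 states: "The primary and secondary endpoints will be reported based on the AT Population". Under Analysis Sets in Section 8.6, AT is "all patients that were enrolled in the trial for whom the SAPIEN 3 valve implant procedure was begun", and the Valve Implant (VI) population is "all AT patient who received and retained the SAPIEN 3 valve upon leaving the procedure room". A later explant removes a patient from neither set. The primary endpoint (Section 7.1.6) is death from any cause by day 30, estimated by Kaplan-Meier with Greenwood standard errors (Section 8.4).

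**The concern.** The analysis needs every AT patient's status at day 30. The explant rule ties the end of observation to something else, the resolution of adverse events, which can happen earlier. The rule just before it names the 30-day assessment and this one does not, so a site could take the difference as intended. Sites could also apply different exit rules.

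At stake are the primary endpoint for patients who lost the device and their non-fatal 30-day clinical events. Leaving after an explant is unlikely to be unrelated to prognosis, so the usual Kaplan-Meier assumption of uninformative censoring is doubtful for them. No later analysis rule can recover vital status that was never collected.

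**Working it through.** **1. The plan's own figure.** Section 8.3 expects drop-out below 17%. With up to 60 treated and at least 50 completing day 30, (60 − 50)/60 = 16.7%, so the figure reproduces. It is a headcount allowance of up to 10 patients.

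**2. The rules side by side.**

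| Patient | In AT | In VI | Followed until | Day 30 named in the exit rule |
|---|---|---|---|---|
| Never retained the valve | yes | no | 30-day assessment or AE resolution; recheck at day 44 if an AE is ongoing | yes |
| Explanted after leaving the procedure room | yes | yes | AE resolution | no |

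For day-30 status to go unobserved, three things must coincide: the explant falls before day 30, all adverse events resolve before day 30, and the site treats the exit rule as overriding the 30-Day Visit section. A death while an adverse event is still open would be captured.

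**3. Range of the primary estimate.** With d observed deaths and u AT patients of unknown status, the day-30 proportion lies between d/N and (d + u)/N, so the width is u/N. The documents give no explant rate, so d and u are assumptions.

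- u = 1: 1/50 = 2.00 points; 1/60 = 1.67 points.
- d = 1, u = 1: 2.0% to 4.0% at N = 50; 1.7% to 3.3% at N = 60.

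N can slightly exceed 60, because Section 7.1.5.1 counts toward the 60 only patients who leave the room with the valve in place.

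**4. What Kaplan-Meier would report.** Section 8.4 does not name the form of the limits, so plain 95% limits are assumed: estimate + 1.96 × SE for the upper limit, with the lower limit cut at 0.

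*Downward error: a death after exit is missed.*

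| N | True deaths | Complete follow-up (upper limit) | One death missed (upper limit) |
|---|---|---|---|
| 50 | 3 | 6.00% (12.6%) | 4.00–4.08% (9.4–9.6%) |
| 60 | 3 | 5.00% (10.5%) | 3.33–3.39% (7.9–8.0%) |
| 50 | 1 | 2.00% (5.9%) | 0%, interval has no width |
| 60 | 1 | 1.67% (4.9%) | 0%, interval has no width |

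At N = 50 the lower figure is 1 − (49/50)(48/49) = 4.00% (exit after the other deaths), and the higher is 1 − (48/49)(47/48) = 4.08% (exit before them).

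*Upward error: survivors leave before another patient's death (one death).*

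- N = 50: 1/50 = 2.00% becomes 1/49 = 2.04% with one exit and 1/47 = 2.13% with three. The upper limit goes from 5.9% to 6.0% and 6.3%.
- N = 60: 1/60 = 1.67% becomes 1/59 = 1.69% and 1/57 = 1.75%. The upper limit goes from 4.9% to 5.0% and 5.2%.

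A survivor who leaves after the last death does not change the estimate.

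**The case against.** The strongest reply is that the plan already covers this. The 30-Day Visit section applies to all patients, and Follow-Up Visits opens by calling for rigorous follow-up to determine the endpoints. An explant can happen at any time in five years, so the exit rule may only be meant to end long-term follow-up. That is a fair reading and may be the intended one. However, the visit section does not say that it overrides the specific exit instruction, and a site that followed the exit rule literally would not be departing from its wording.

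Other sections help only in part.

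- **Section 13.1** runs adverse event reporting until participation ends, which it explains as study completion or withdrawal of consent. It does not settle whether a protocol exit counts as completion.
- **Section 8.3** allows for drop-out, but that protects the number completing, not against loss that may depend on outcome.
- **Section 9.2** promises tracking during follow-up, which an exit may end.
- **Section 8.5** defers detail to a separate SAP, which is not in the text available here. It may already say how early exits are censored, but it cannot supply data that were not collected.

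Three stronger readings are tempting, and the documents do not support them.

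- **That the protocol directs exit before day 30.** Given the 30-Day Visit section, it may permit this; it does not clearly require it.
- **That patients who never retained the valve are lost in the same way.** The conjunction in their rule is loose, but the day-44 recheck presupposes a 30-day visit.
- **That every 30-day endpoint is exposed.** Valve-performance measures cannot apply to a removed valve, and the explant itself precedes the exit. What is exposed is vital status and non-fatal clinical events.

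The objection that the situation is rare also stands, and it limits the size of the point.

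**Conclusion.** The point holds as an unreconciled wording between the explant exit rule and the 30-Day Visit section, with a possible consequence for the primary endpoint. It is minor. The effect is zero if no AT patient leaves before day 30, and probably small otherwise. The error can run either way, but the larger risk is a missed death, worth about 2 points on the estimate at N = 50. The counts of deaths and exits behind these figures are assumptions. Section 8 sets no success threshold, so the consequence is confined to the estimate, its interval and the reported 30-day events.

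**What to change.** Reconcile the explant rule with the 30-Day Visit section and Sections 8.4 and 8.6. Possible wording for Follow-Up Visits: *AT patients whose valve is explanted before day 30 have vital status and clinical endpoint events ascertained through day 30 before study exit, whatever the AE status, unless consent is withdrawn or the patient is lost to follow-up.*

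In Section 8.4, state that explant is not a censoring event for 30-day mortality, and report the number of AT patients whose day-30 vital status is unknown.

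This changes only when data collection may stop; it alters no treatment and leaves the sample size as it is. The cost is one day-30 contact for a few patients, with consent wording to match.

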### 30-Day Visit

All patients will undergo the following assessments within the 30-Day follow-up period +14 days):

- Pertinent physical examination [include blood pressure, weight and all major systems findings]
- Adverse events
- Current cardiac medications and all medications given for cardiovascular effect
- NYHA functional classification
- CSS Angina Classification
- Neurological assessments
  - NIHSS
  - mRS
- 6 Minute Walk Test (6MWT)
- KCCQ
- Clinical Laboratory Test
  - Blood count (hemoglobin, hematocrit, platelet count, white blood cells)
  - Creatinine
  - CK/CK-MB and/or troponins
  - Albumin
- 12-Lead ECG
- Comprehensive TTE. If not adequate, a TEE will be performed

For patients with abnormal findings related to valve integrity and position and patients with adverse events related to worsening valve function, fluoroscopic imaging of the implanted valve will be completed.

### 6 Month Visit

All patients will undergo the following assessments within the 6 Month follow-up period:

- Adverse events
- Current cardiac medications and all medications given for cardiovascular effect

The 6 month visit may be completed via a telephone conversation with a delegated study team member. The telephone call must be documented in the patient's study records.

### 1 Year Visit

All patients will undergo the following assessments within the 12 Month follow-up period:

- Pertinent physical examination [include blood pressure, weight and all major systems findings]
- Adverse events

- Current cardiac medications and all medications given for cardiovascular effect
- NYHA functional classification
- CSS Angina Classification
- 12-Lead ECG
- Comprehensive TTE. If not adequate, a TEE will be performed

For patients with abnormal findings related to valve integrity and position and patients with adverse events related to worsening valve function, fluoroscopic imaging of the implanted valve will be completed.

